5.0 Treatment Plan

5.1 Schedule

Patients are randomized between 2 treatment arms:

Induction:

- A) SGI-110 60mg/m² subcutaneously (SQ) daily x 5
- B) SGI-110 60 mg/m² SQ daily x 5 + idarubicin 6mg/m² IV daily x 2

Cycles will be repeated every 4 to 6 weeks or longer as indicated by leukemia recurrence or recovery of normal hematopoiesis. Since efficacy from epigenetic treatment with agents such as SGI-110 may take longer to manifest, it is recommended that patients receive at least 2 courses of the above regimens regardless of their response.

If a patient does not achieve a CR or CR_i after a maximum of 3 induction courses, the patient will be taken off study unless the patient is deriving clinical benefit at which time continuation of protocol therapy will be allowed with prior PI approval.

Maintenance:

Patients who achieve a CR or CR_p during induction may receive up to 24 months of maintenance therapy every 4 to 8 weeks. The maintenance arm will be the same as the induction arm e.g. patients who are induced on SGI-110 + idarubicin are also maintained with SGI-110 + idarubicin.

- A) SGI-110 60mg/m² SQ daily x 5**
- B) SGI-110 60mg/m² SQ daily x 5 + idarubicin 6 mg/m² IV on Day 1**

- Patient may receive follow up laboratory tests from their local physician.
- All protocol-specific treatment decisions will be made by MD Anderson physician.
- The PI/treating physician must review all outside lab results, determine the clinical significance and sign/date the report.

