7.0 Evaluation during Study

On Day 1 (+/- 7 days) of every cycle, the following tests and procedures will be performed:

- You will have a physical exam, including measurement of your weight
- Vital signs.
- Your performance status will be recorded.

CBC with differential and platelet counts at least once a week until remission, then every 2 to 4 weeks during therapy, and every 4 to 8 weeks thereafter as long as on study. No differential is needed if the WBC is $< 1.0 \times 10^9/L$.

Chemistry profile (at least creatinine, SGOT or SGPT, total bilirubin) at least weekly until remission, then every 4 to 8 weeks during therapy.

Bone marrow aspirate and/or biopsy starting on day 28 (± 7 days) of therapy and then every 2 weeks (± 7 days) as required by leukemia evolution until remission or non-response. Bone marrow tests can be ordered more frequently if mandated by development of peripheral blood counts. No repeat bone marrow is necessary if non-response or progressive disease can be unequivocally diagnosed from peripheral blood tests, or, in patients with a WBC ≤ 0.3 if the bone marrow test is considered non-contributory by the investigator at any time point (± 2 days).

LVEF every 3-4 cycles as indicated.

Optional. Blood 10cc pre-treatment, on Days 1 and 15 (+/- 2 days) of the first course to evaluate epigenetic modulation. (This will cover both the 5-day and 10-day regimens)

Follow-up Visits

After your last dose of study drug (after completion of all therapies), you will have follow-up visits. You will only have these visits if the disease has responded to the study drug. This can be done at home through your local cancer doctor as indicated (usually visit + routine CBC and chemistries every 2-3 months). Approximately every 6 months, you will return to Houston for a physical exam and blood (about 1 tablespoon) will be drawn for routine tests:

Chemistry profile (at least creatinine, SGOT or SGPT, total bilirubin).

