8.0 Criteria for Response

8.1 Complete Remission (CR):

. Neutrophil count $\geq 1.0 \times 10^9/L$ and platelet count $\geq 100 \times 10^9/L$, and normal bone marrow differential ($\leq 5\%$ blasts)

8.2 Complete Remission without blood count recovery (CRI): Peripheral blood and bone marrow results as for CR, but with platelet counts of $< 100 \times 10^9/L$ or ANC $< 1.0 \times 10^9/L$

8.3 Partial Remission (PR):

Blood count recovery as for CR, but with both a decrease in marrow blasts of at least 50% and not more than 6 to 25% abnormal cells in the marrow.

8.4 Early mortality: Death within 14 days of first dose.

8.5 Patients who achieve a CR or CR_p during induction may receive up to 24 months of maintenance therapy every 4 to 8 weeks

8.6 Prior to each maintenance cycle, the ANC should be $\geq 1.0 \times 10^9/L$ and the platelet count $\geq 60 \times 10^9/L$, except for patients who are considered to have achieved a CRp following induction and in whom a platelet count of $< 60 \times 10^9/L$ will be allowed to continue.

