9.0 Criteria for Discontinuation of Therapy

Patients can be discontinued from the study under the following conditions:

- 9.1 Patient's physician considers a change of therapy would be in the best interest of the patient.
- 9.2 Patient requests discontinuation or withdraws consent.
- 9.3 There is unacceptable toxicity (e.g., grade 4 nonhematologic toxicity), not controlled with dose adjustments.
- 9.4 There is a need for any treatment not allowed by the protocol.
- 9.5 Investigator determines that the patient has progressive disease after sufficient induction therapy.

Every 6 months, you will return to Houston for a physical exam and blood (about 1 tablespoon) will be drawn for routine tests.

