10.0 Statistical Considerations

10.1.1 Update of the General Description/Sample Size February 01, 2017

This is a Phase II with 2 parallel arms study of SGI-110 in patients with newly diagnosed AML ≥ 70 years of age. The primary objective is to obtain an initial assessment of efficacy for the two SGI-110 regimens in this patient group:

- 1) SGI-110 single-agent for 5 days.
- 2) SGI-110 for 5 days combination with idarubicin for 2 days.

For each arm, we will enroll 20 patients. When all the arms have 20 patients then to be able to enroll more patients after the first 20 patients they have to satisfy the following rules: 1) there is more than 95% chance that the grade 3-4 non-hematological toxicity rate doesn't exceed 30%. 2) there is less than 10% chance that the 8-week mortality exceeds 15% and 3) there is more than 2.5% chance that the CR rate (CR+CRi) is more than 30%.

The arm or arms with the satisfying monitor rules above will continue to enroll an additional 20 patients. This will be decided through an interim analysis discussion with the Leukemia experts and the modality experts coordinating the study.

Complete Remission monitoring

The primary endpoint is the complete remission rate (CRR) evaluated after at least 2 cycles but would also be evaluated after 4 and 6 cycles if the patient is stable or improving. We have a target CRR of 30%, while a CRR of 15% is considered unacceptable. We will monitor complete remission using the Bayesian approach of Thall et al. [19]. The probability of complete remission

is denoted by P_{CR} . We assume $P_{CR} \sim \text{beta}(0.6, 1.4)$. Our stopping rule is given by the following probability statement: $\Pr(P_{CR} > 0.30 | \text{data}) < 0.025$. That is, we will stop the study if, at any time during the study, we determine that there is less than 2.5% chance that the CRR is more than 30%. This stopping rule will be applied in each arm. The stopping boundaries for complete remission, based on these assumptions and monitoring conditions are found in **Table 1**. We will apply these stopping boundaries starting from the first patient and in cohorts of 10. For example, accrual will cease if only 2 patients experiences complete remission among in the first 20 patients treated. The operating characteristics are summarized in **Table 2**. Both the decision rule and operating characteristics were calculated using the stopbound procedure in Stata version12.1.

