Table 1. Stopping boundaries for Complete Remission (separately for each arm)

The number of patients evaluated for complete remission	10	20	30	40
The number of patients with complete remission	0	</=2	</=4	</=6

Table 2. Operating characteristics for Complete Remission (separately for each arm)

True Complete Remission Rate	Early Stopping Probability	Sample Size		
		25 th percentile	Median	75 th percentile
0.15	0.5994	20	30	40
0.20	0.3303	30	40	40
0.25	0.1528	40	40	40
0.30	0.0670	40	40	40
0.35	0.0255	40	40	40
0.40	0.0087	40	40	40

Toxicity Monitoring

We will monitor toxicity using the Bayesian approach of Thall et al. [19]. **A toxicity is defined as grade 3 or higher non-hematological toxicity occurring during the first two cycles.** Following are the rules for the monitoring of toxicities. The probability of toxicities is denoted by P_T . We assume $P_T \sim \text{beta}(0.6, 1.4)$. Our stopping rule is given by the following probability statement: $\Pr(P_T > 0.30 | \text{data}) > 0.95$. That is, we will stop the study if, at any time during the study, we determine that there is more than 95% chance that the toxicity is more than 30%. This stopping rule will be applied in each arm. The stopping boundaries for toxicities, based on these assumptions and monitoring conditions is found in **Table 3**. We will apply these stopping boundaries starting from the first patient and in cohorts of 5. For example, accrual will cease if 4 patients experiences toxicities among in the first 5 patients treated. The operating characteristics are summarized in **Table 4**. Both the decision rule and operating characteristics were calculated using the stopbound procedure in Stata version12.1.

Table 3. Stopping boundaries for Toxicities (separately for each arm)

The number of patients evaluated for toxicities	5	10	15	20	25	30	35	40
The number of patients with toxicities	4	6	8	10	12	14	16	18

Table 4. Operating characteristics for Toxicity Monitoring (separately for each arm)

True Toxicity Rate	Early	Sample Size
--------------------	-------	-------------

Stopping Probability		25 th percentile	Median	75 th percentile
0.10	0.0005	40	40	40
0.20	0.0149	40	40	40
0.30	0.1247	40	40	40
0.40	0.4581	15	40	40
0.50	0.8272	10	15	40

Mortality Monitoring

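### Must the plan say which response assessment decides the complete remission rate, and how patients still on induction enter a look?

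*Combined protocol and SAP*

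**What the plan says.** The combined protocol and SAP deals with this in several places.

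- **Section 10.1.1, Complete Remission monitoring.** The CRR (CR + CRi) is "evaluated after at least 2 cycles but would also be evaluated after 4 and 6 cycles if the patient is stable or improving". The target is 30% and the unacceptable rate 15%. The prior is beta(0.6, 1.4), and an arm stops if Pr(P_CR > 0.30 | data) < 0.025, with looks in cohorts of 10.
- **Table 1** indexes its bounds (0, 2, 4 and 6 remissions at 10, 20, 30 and 40 patients) by "The number of patients evaluated for complete remission". The worked example says that "accrual will cease if only 2 patients experiences complete remission among in the first 20 patients treated".
- **Section 5.1** sets the limit on induction: "If a patient does not achieve a CR or CR_i after a maximum of 3 induction courses, the patient will be taken off study", with the exception "unless the patient is deriving clinical benefit at which time continuation of protocol therapy will be allowed with prior PI approval".
- **Section 7.0** schedules marrows from day 28 and then "as required by leukemia evolution until remission or non-response".
- **Section 9.0** lists among its reasons for discontinuation: "Investigator determines that the patient has progressive disease after sufficient induction therapy".
- **The Statistical Analysis Plan paragraph** includes everyone who received at least one dose in the efficacy analysis.
- **Section 2.4** reports complete responses in 4 of 8 patients on 5-day SGI-110 and 7 of 8 on SGI-110 plus idarubicin. It continues these two arms under the same Bayesian design.

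**The concern.** Three assessment times are named for the primary endpoint and none is said to decide it. If only the cycle-2 assessment counted, later remissions would be lost. With a true eventual CRR of 30%, and 90%, 80%, 70% or 50% of remissions present by cycle 2 (assumed fractions), early stopping would be 11.3%, 18.5%, 29.0% or 59.3%, against 6.6% under best response.

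The denominator raises a similar worry. At 4 to 6 weeks per cycle, three courses take 12 to 18 weeks, and Section 5.1 allows longer intervals. Some of the first 20 treated patients may therefore have no final response when a look falls due. With 2 remissions, counting all 20 gives a posterior probability of 0.0153, which stops the arm. Counting only 18 evaluated patients gives 0.0271, which does not meet the threshold. One word could seem to decide whether an arm closes.

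The ways in which induction ends also look inconsistent: three courses in Section 5.1, assessments at 4 and 6 cycles in Section 10.1.1, sufficient induction in Section 9.0, and an undefined non-response in Section 7.0.

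**Working it through.** **1. Reproduce the plan's figures.** After x remissions in n patients the posterior is beta(0.6 + x, 1.4 + n − x). Pr(P_CR > 0.30) at each bound, and with one more remission, is:

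| n | at the Table 1 bound | one more remission |
|---|---|---|
| 10 | 0 remissions: 0.0065 | 0.063 |
| 20 | 2 remissions: 0.0153 | 0.056 |
| 30 | 4 remissions: 0.0152 | 0.044 |
| 40 | 6 remissions: 0.0130 | 0.033 |

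The threshold of 0.025 lies between the two columns in every row, so Table 1 is exact. An exact binomial recursion over looks at 10, 20 and 30 (crossing the bound at 40 is not early stopping), with all outcomes known, gives:

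| True CRR | 0.15 | 0.20 | 0.25 | 0.30 | 0.35 | 0.40 |
|---|---|---|---|---|---|---|
| Recomputed | 0.593 | 0.332 | 0.157 | 0.066 | 0.0255 | 0.0094 |
| Table 2 | 0.5994 | 0.3303 | 0.1528 | 0.0670 | 0.0255 | 0.0087 |

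Table 2 therefore assumes that every counted patient has a known outcome. This does not favour either label: the first 20 treated, looked at once their responses are known, are also the first 20 evaluated.

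**2. Which assessment counts.** A cycle-2-only reading would leave the evaluations at 4 and 6 cycles without purpose. Section 7.0 samples marrow until remission or non-response, and Section 5.1 accepts a remission reached in any of up to three courses. All of this fits best response on protocol therapy. The at-least-one-dose population keeps early deaths and dropouts in the denominator as non-remissions.

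**3. The end of induction.** Only Section 5.1 sets a limit. The 4- and 6-cycle points are assessment times for stable or improving patients, and the clinical-benefit exception gives them a place beyond three courses. The Section 9.0 item concerns progressive disease, which is a different event. Non-response in Section 7.0 belongs to a sampling schedule and plainly means that the Section 8.0 response criteria are not met. The sections are compatible.

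**4. Effect on decisions, if the Section 2.4 counts carry forward.**

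- *Condition for expanding beyond 20 patients*, Pr(P_CR > 0.30) > 0.025. With no further remission in the next 12 patients, the single-agent arm stands at 4/20, giving 0.146. The idarubicin arm stands at 7/20, giving 0.658. Both pass, however pending patients are counted.
- *Idarubicin arm.* Seven remissions exceed every bound in Table 1, the largest being 6.
- *Single-agent arm.* Four remissions exceed the bounds at 10 and 20. The bound of 4 at 30 is reached only if the next 30 − 8 = 22 patients have no remission. If k of the 22 are pending and counted as failures, the chance is (1 − p)^(22 − k):

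| k (assumed) | true CRR 30% | true CRR 20% |
|---|---|---|
| 0 | 0.04% | 0.7% |
| 5 | 0.2% | 2.3% |
| 10 | 1.4% | 6.9% |

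The rows for k = 5 and 10 are upper bounds for those k: marrows start at day 28, so some recent entrants in remission would already be known.

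**5. If the earlier counts did not carry forward.** From zero patients, with the last 2 or 4 entered at each look pending and counted as failures, early stopping at a true CRR of 30% rises from 6.6% to at most 11.3% or 19.4%. This requires an analyst to score an unassessed patient as a failure, which the plan nowhere asks.

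**The case for a change.** The best argument for a change is that the CRR differs from the other monitored endpoints. Toxicity has a window of two cycles and mortality one of 8 weeks, so for them *evaluated* and *treated* soon coincide. The CRR window is open, and it is the primary endpoint. Responses by arm are already known, so an unwritten rule leaves room to choose the cycle or denominator afterwards. A few sentences would close the gap.

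Part of this stands: the plan states neither best response nor a rule for pending patients. But neither Table 1 nor its example gives a competing rule. The example only illustrates the table, and Tables 3 and 5 have the same change of word. The room for later choice is small, because the dosed population is fixed and the later assessments are written in. Expansion beyond 20 patients is also settled in an interim discussion among the study's experts, where pending patients would be visible.

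The obvious repair could also do harm. Counting only patients whose status is settled favours remissions, which settle sooner than failures. Suppose remission settles at 6 weeks and non-remission at 18, patients enter evenly, and accrual runs on to 40. Early stopping at a true CRR of 15% then falls to about 0.52 with one patient per arm every 4 weeks and about 0.43 with two, against 0.593 when looks take patients in entry order and wait. The settling times and accrual rates are assumptions.

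**Conclusion.** The concern does not call for a change. The plan leaves out a detail that analysts fill sensibly: best CR or CRi on protocol therapy, all dosed patients in the denominator, and looks taken in entry order once responses are known. Under that reading Table 1 reproduces exactly, Table 2 to within 0.007, and the final CRR is sound. The change from *evaluated* to *treated* is loose wording.

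The practical effect is negligible. The remission condition at 20 patients is met in both arms, the idarubicin arm is beyond every bound, and the chance of an early stop in the single-agent arm at a true CRR of 30% is 0.04%, and at most 1.4% with 10 pending patients scored as failures.

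This rests on four assumptions: the Section 2.4 patients count towards the 40 per arm; their responses are settled; the complete responses reported there are the monitored endpoint (if CRi was left out, the monitored count can only be higher); and the numbers pending are illustrative, because the documents give no accrual rate. The first matters most. Without it the theoretical effect is larger, as the from-zero figures show, but still only if pending patients are scored as failures.

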We will monitor 8-week mortality using the Bayesian approach of Thall et al. [19]. Following are the rules for the monitoring of 8-week mortality. The probability of 8-week mortality is denoted by P_M . We assume $P_M \sim \text{beta}(0.3, 1.7)$. Our stopping rule is given by the following probability statement: $\Pr(P_M > 0.15 | \text{data}) > 0.90$. That is, we will stop the study if, at any time during the study, we determine that there is more than 90% chance that the 8-week mortality is more than 15%. This stopping rule will be applied in each arm. The stopping boundaries for 8-week mortality, based on these assumptions and monitoring conditions is found in **Table 5**. We will apply these stopping boundaries starting from the first patient and in cohorts of 5. For example, accrual will cease if 3 patients died during the first 8 weeks among in the first 5 patients treated. The operating characteristics are summarized in **Table 6**. Both the decision rule and operating characteristics were calculated using the stopbound procedure in Stata version12.1.

Table 5. Stopping boundaries for Mortality (separately for each arm)

The number of patients evaluated for mortality	5	10	15	20	25	30	35	40
The number of patients died during the first 8 weeks	3	4	5	6	7	8	9	10

Table 6. Operating characteristics for Mortality Monitoring (separately for each arm)

True Mortality Rate	Early Stopping Probability	Sample Size		
		25 th percentile	Median	75 th percentile
0.05	0.0029	40	40	40
0.10	0.0298	40	40	40
0.15	0.1552	40	40	40
0.20	0.3790	20	40	40
0.25	0.6341	10	25	40

Statistical Analysis Plan

All patients who received at least 1 dose of the agent will be included in the intent-to-treat analysis for efficacy and safety. Demographic/clinical characteristics and safety data of the patients will be summarized using descriptive statistics such as mean, standard deviation, median and range (i.e. remission duration). Complete remission rates (CRR) will be presented with 95% confidence intervals. The association between CRR and patient and clinical characteristics will be

examined by Wilcoxon's rank sum test or Fisher's exact test. Survival time will be estimated using the Kaplan-Meier method. Patients who drop out of the study will be included in the time to event data as "censored data". The two-sided log-rank test will be used to assess the differences of time to events between groups.

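### Table 4, toxicity 0.50 row: a 75th-percentile sample size of 40 contradicts the 0.8272 early-stopping probability beside it (it should be 30), and no table shows the three stopping rules acting together

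*Combined protocol and SAP*

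**What the plan says.** Section 10.1.1 sets three Bayesian stopping rules (complete remission, toxicity, 8-week mortality) and applies each of them in each arm. An arm enrols 20 patients and may enrol 20 more, so the maximum is 40.

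- **Toxicity rule.** The arm stops if "we determine that there is more than 95% chance that the toxicity is more than 30"%. The prior is beta(0.6, 1.4). On timing the plan says: "We will apply these stopping boundaries starting from the first patient and in cohorts of 5. For example, accrual will cease if 4 patients" have toxicity among the first 5. The Table 3 boundaries, at 5, 10, ..., 40 patients, are: "The number of patients with toxicities 4 6 8 10 12 14 16 18".
- **Table 4, last row.** The table is titled "Operating characteristics for Toxicity Monitoring (separately for each arm"). Its last row reads "0.50 0.8272 10 15 40": true rate, early-stopping probability, then the 25th, 50th and 75th percentiles of sample size.
- **The other two rules.** Each has its own table: "Operating characteristics for Complete Remission (separately for each arm") is Table 2 and "Operating characteristics for Mortality Monitoring (separately for each arm") is Table 6. There is no table for the three rules in combination.
- **Expansion at 20 patients.** The sample-size paragraph of the same section sets three conditions for going beyond 20: more than a 95% chance that toxicity does not exceed 30%, less than a 10% chance that 8-week mortality exceeds 15%, and more than a 2.5% chance that the remission rate is above 30%.

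**The concern.** Two entries in one row of Table 4 cannot both be true. The wrong one sits in the safety table's worst scenario, and taken alone it suggests that at least a quarter of arms with 50% toxicity would run to full size.

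The second matter is one of coverage. An arm stops when any one of three rules is met, but each table follows a single rule. A reader who wants the chance that an arm closes early, or its likely size, cannot find it. These tables are the plan's only quantitative account of how the monitoring behaves.

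**Working it through.** **Inputs.** Boundaries from Tables 1, 3 and 5; true rates and printed values from Tables 2, 4 and 6; priors and thresholds from the text of section 10.1.1.

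**1. Boundaries.** After x events in n patients, the posterior for a beta(a, b) prior is beta(a + x, b + n − x). For toxicity at n = 5, Pr(P_T > 0.30) is 0.8745 with 3 events and 0.9751 with 4, so the boundary is 4, as printed. All entries in Tables 1, 3 and 5 reproduce in this way.

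**2. Printed stopping probabilities.** For each rule alone, the distribution of the event count is carried from look to look and the part that meets the boundary is removed. At toxicity 0.50:

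- n = 5: P(at least 4 of 5) = 6/32 = 0.1875.
- n = 10: arms still open with 1, 2 or 3 events need at least 5, 4 or 3 more, giving (5×1 + 10×6 + 10×16)/1024 = 225/1024 = 0.2197.

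Continuing:

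| Patients | 5 | 10 | 15 | 20 | 25 | 30 | 35 |
|---|---|---|---|---|---|---|---|
| Stop at this look | 0.1875 | 0.2197 | 0.1516 | 0.1048 | 0.0748 | 0.0549 | 0.0412 |
| Stopped by now | 0.1875 | 0.4072 | 0.5588 | 0.6636 | 0.7384 | 0.7933 | 0.8345 |

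The exact probability of stopping before 40 is 0.8345, against 0.8272 printed. All 16 probabilities in Tables 2, 4 and 6 reproduce within 0.8 of a percentage point on this definition (for example, Table 2 at 0.15: 0.5929 against 0.5994; Table 6 at 0.25: 0.6364 against 0.6341). If a stop at patient 40 also counted as early, the toxicity figure would be 0.8661, a worse fit. So 0.8272 means stopping before 40.

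**3. The percentile.** From the printed row alone, only 1 − 0.8272 = 17.3% of arms reach 40, so the 75th percentile is below 40. From the table above, 0.7384 have stopped by 25 and 0.7933 by 30, so it is **30**. The printed 25th percentile and median (10 and 15) agree with the recursion. In 300 repeat simulations at each of 1,000, 5,000 and 10,000 arms, the 75th percentile lay between 25 and 30 and was never 40.

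**4. Three rules together,** at remission 0.30, toxicity 0.30 and mortality 0.15. The exact single-rule probabilities are 0.0660, 0.1231 and 0.1527 (printed: 0.0670, 0.1247, 0.1552).

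- Independent outcomes: 1 − (0.9340 × 0.8769 × 0.8473) = 0.306. Cumulative joint stopping is 0.241 by 20 and 0.264 by 25, so the 25th percentile of sample size is 25, where all three tables print 40.
- Any dependence: at least the largest single value, 0.153, and at most the sum, 0.342.
- One assumed dependence (early deaths never in remission and always counted as toxicity), by simulation: 0.255.
- Lower risk, independent: 0.111 at remission 0.30, toxicity 0.20, mortality 0.10; 0.012 at 0.40, 0.10, 0.05.

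**5. The expansion conditions at 20 patients.** Step 4 uses only the stopping boundaries. Read literally with the stated priors, the expansion conditions are much tighter for toxicity and mortality:

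- Toxicity: Pr(P_T ≤ 0.30) is 0.985 with 2 of 20 and 0.944 with 3 of 20. At most 2 are allowed; Table 3 stops at 10.
- Mortality: Pr(P_M > 0.15) is 0.058 with 1 of 20 and 0.212 with 2 of 20. At most 1 is allowed; Table 5 stops at 6.
- Remission: this condition is the converse of the stopping rule, so it agrees with Table 1.

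With the literal conditions added, again under independence, the chance of not reaching 40 is about 99% at 0.30/0.30/0.15 and about 92% at 0.30/0.20/0.10.

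**The case against.** The best defence is that the tables do what their headings say. Each is headed for one endpoint, nothing in section 10.1.1 presents it as the combined probability, and the probabilities are accurate for that purpose. The one bad cell feeds no boundary, prior, threshold or sample size, and the 0.8272 and the median of 15 in the same row already tell the reader that most such arms stop early. All of this stands. It makes the cell an erratum and the joint table an omission.

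A reader might infer more: that the stopping probabilities and arm sizes in all three tables are wrong. The documents do not support that. The probabilities reproduce, and the 20 + 20 arm size is set in the text and not derived from these tables.

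Nor is Table 6 at mortality 0.25 a second error. It prints a 25th percentile of 10 where the exact value is 15, but the exact probability of stopping by 10 patients is 0.245, so close to 0.25 that ordinary simulation error explains the difference.

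It is also fair to say that 31% is not the arm's actual stopping chance. It assumes independence, which the documents neither state nor deny, and it leaves out the expansion conditions at 20 patients.

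**Conclusion.** One cell is wrong: the 75th percentile in the 0.50 row of Table 4 should be 30. This follows from the row itself and from Table 3 and needs no outside assumption. No boundary or stopping rule is affected.

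Separately, the plan omits joint operating characteristics. Single-rule figures understate total stopping materially at the reference rates (about 31% under independence, limits 15% to 34%) and little when toxicity and mortality are low. These figures count stops before patient 40 under the boundaries of Tables 1, 3 and 5 only. They cannot be final until the 20-patient conditions are reconciled with Tables 3 and 5, since the literal reading changes them several-fold.

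**What to change.** 1. In Table 4, row 0.50, change the 75th percentile from 40 to 30.
2. Label Tables 2, 4 and 6 as the behaviour of each rule acting alone. No entry in Table 6 needs to change.
3. Reconcile the expansion conditions at 20 patients with the n = 20 boundaries in Tables 3 and 5, and state which governs. That decision belongs to the study team.
4. Then add one table of early-stopping probability and sample-size percentiles with all three rules active, over a few combinations of true rates. State the assumed dependence between remission, toxicity and early death, and show the range across alternatives.

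Items 1, 2 and 4 cost a short recalculation and some text, need no patients and leave the design as it is. Item 3 needs a decision and a clarifying amendment.

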1.0 Objectives

- 1.1 To determine the complete remission (CR) rate, remission duration, leukemia-free survival, and survival in patients ≥ 70 years with previously untreated AML with 4 different SGI-110 single agent and SGI-110 based combination regimens.
- 1.2 To determine the safety profile and tolerability of the 4 SGI-110 single agent and SGI-110 based combination regimens in patients ≥ 70 years of age with previously untreated AML.

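### Remission duration is assigned to a raw mean, SD, median and range instead of Kaplan-Meier, so its mean is too low whenever remissions are ongoing at cut-off

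*Combined protocol and SAP*

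**What the plan says.** Objective 1.1 lists the efficacy outcomes as the CR rate together with "remission duration, leukemia-free survival, and survival in patients" aged 70 or older.

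The Statistical Analysis Plan paragraph at the end of Section 10.1.1 has four relevant sentences:

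- Demographic, clinical and safety data will be "summarized using descriptive statistics such as mean, standard deviation, median and range (i.e. remission duration"). Section 10 names remission duration nowhere else.
- "Survival time will be estimated using the Kaplan-Meier method". No other endpoint is named for this method.
- "Patients who drop out of the study will be included in the time to event data", as censored observations. Patients still on study and event-free at cut-off are not mentioned.
- "The two-sided log-rank test will be used to assess the differences of time to events between groups". The endpoints to be tested are not listed.

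Section 5.1 says that responders "may receive up to 24 months of maintenance therapy every 4 to 8 weeks". The documents give no data cut-off date, no minimum follow-up, and no start, end or censoring rule for remission duration.

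**The concern.** Remission duration is a time-to-event outcome. A patient in continuing remission when the data are cut contributes only a lower bound, and with up to two years of maintenance such patients are to be expected. Means, SDs, medians and ranges have no place for a lower bound. The analyst must either count the ongoing duration as complete or leave the patient out, and both choices pull the mean down.

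At stake is the per-arm description of how long remissions last. Section 2.3 says the study is meant to help the design of a Phase III trial, so an understated duration could be carried forward. Remission duration is not the primary endpoint, and no stopping or expansion rule uses it.

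**Working it through.** The plan gives no figure for remission duration, so there is nothing to reproduce. The check covers the direction of the bias and then its size under stated assumptions.

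**Direction.** Let T be the true remission duration and C the follow-up available from remission. The recorded duration is min(T, C), which never exceeds T. If any remission is ongoing, the mean of the recorded durations is therefore below the mean of T. Leaving ongoing remissions out keeps the shorter durations preferentially, and this lowered the mean in every scenario run.

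**Assumptions (not from the documents).** T is exponential with mean μ = median / ln 2. C is a minimum follow-up a plus a uniform 0 to 24 months of staggered entry. True medians of 12 and 6 months are shown. The only duration figure in the documents (Section 2.1, for 3+7 at age 60 or older) is that remissions rarely last beyond 12 months.

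**Formula.** The proportion still in remission at cut-off is q = (μ/24) × [exp(−a/μ) − exp(−(a+24)/μ)], and the expected raw mean is μ × (1 − q). Under this model the proportional bias of the raw mean equals −q.

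**Worked case: true median 12, a = 12.** μ = 12 / 0.6931 = 17.31. The exponentials are 0.5 and 0.125. q = (17.31/24) × 0.375 = 0.2705. Raw mean = 17.31 × 0.7295 = 12.63 months.

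**Worked case: true median 6, a = 12.** μ = 8.66. The exponentials are 0.25 and 0.0156. q = (8.66/24) × 0.2344 = 0.0845. Raw mean = 8.66 × 0.9155 = 7.92 months.

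All scenarios, in months. The raw means come from the formula; the other columns come from simulation with 1,000,000 durations per scenario, which also agreed with the formula:

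| True median (mean) | Minimum follow-up | Ongoing | Raw mean, all responders | Raw median, all responders | Median, relapsed only |
|---|---|---|---|---|---|
| 12 (17.3) | 3 | 45% | 9.4 | 8.0 | 5.7 |
| 12 (17.3) | 6 | 38% | 10.7 | 9.4 | 6.4 |
| 12 (17.3) | 12 | 27% | 12.6 | 12.0 | 7.9 |
| 12 (17.3) | 24 | 14% | 15.0 | 12.0 | 9.8 |
| 6 (8.7) | 3 | 24% | 6.6 | 5.2 | 4.2 |
| 6 (8.7) | 6 | 17% | 7.2 | 6.0 | 4.7 |
| 6 (8.7) | 12 | 8% | 7.9 | 6.0 | 5.3 |
| 6 (8.7) | 24 | 2% | 8.5 | 6.0 | 5.8 |

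The all-responder median is correct once minimum follow-up reaches the true median, because no one can then be censored before that point. The relapsed-only median is low throughout.

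**Other follow-up assumptions.** With C uniform over 3–24, 6–36 or 12–48 months and true medians of 6 to 18 months, the bias in the mean ran from −6% to −61% counting all responders, and from −15% to −73% counting completed remissions only. For 6–36 months and a true median of 12, the large-sample Kaplan-Meier median was 12.0, against raw medians of 9.7 (all responders) and 7.0 (completed only).

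**At the trial's size.** A full arm of 40 at the 30% target CR rate gives 40 × 0.30 = 12 responders. With a true median of 12 months and minimum follow-up of 3/6/12/24 months, the raw mean fell below the true mean in 100/99.9/96/76% of 20,000 simulated trials. The reference value without censoring is about 54%, P(Poisson(12) ≥ 12) = 0.538, because a mean of 12 skewed durations is more often low than high. In the same trials the Kaplan-Meier median had a 5th percentile of about 4.9 months and was not reached in 12/7/1.5/0%.

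**The case against.** The strongest reply is that this is a stray parenthesis. The sentence is about demographic, clinical and safety data, and remission duration is none of these as a baseline or safety variable. Shortly afterwards the plan provides for censored time-to-event data and a log-rank comparison in general terms, which could be read to include remission duration. The wording before the list of statistics makes that list illustrative, so a mean might never be reported. The only duration figure in the documents points to short remissions, for which the bias is modest: at a true median of 6 it is about −8.5% with 12 months' minimum follow-up and −2% with 24. Kaplan-Meier with 12 responders is itself imprecise.

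Much of this stands. A drafting slip is plausible, the size is uncertain, the median is safe with enough follow-up, and the log-rank test handles censoring. But the only method the plan names for this endpoint remains the wrong one. A log-rank test yields no per-arm estimate, and if its sentence does cover remission duration, the plan treats one endpoint in two ways. Neither long follow-up nor short remissions is assured by the documents. Imprecision shows in a confidence interval, whereas the bias of a raw mean does not show at all.

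**Conclusion.** The concern holds. The downward bias of a raw mean over all responders is certain whenever any remission is ongoing at cut-off. For relapsed-only summaries it rests on follow-up being independent of remission length. The size rests on assumed exponential durations and assumed follow-up: in the table it ranges from about 2% (true median 6, 24 months' minimum follow-up) to about 45% (true median 12, 3 months). The all-responder median is biased only when some follow-up is shorter than the true median.

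The consequence is confined to a descriptive estimate of a non-primary efficacy outcome. Leukemia-free survival is not mis-specified; its estimator is simply not stated. The correction should be made, but the trial's design does not depend on it.

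**What to change.** Remove the parenthesis naming remission duration from the descriptive-statistics sentence and add, for example:

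*Remission duration among responders, from first documented CR or CRi to relapse, will be estimated by the Kaplan-Meier method, with the median and 95% confidence interval for each arm. Patients in continuing remission will be censored at their last disease assessment.*

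Three clarifications belong beside it:

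- State whether death in remission counts as an event or as a competing risk, with cumulative incidence in the latter case.
- State that leukemia-free survival, with relapse or death as the event, is also estimated by Kaplan-Meier, so that the two endpoints stay distinct.
- State how relapse is defined and dated. Section 8.0 gives no relapse criterion, and Section 7.0 schedules marrows "as required by leukemia evolution until remission or non-response". It does allow more frequent marrows if blood counts call for them, and it continues blood counts during remission, so those could be used to date relapse.

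The core change is two or three sentences. Sample size, randomization and the monitoring boundaries are unchanged.
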